#### 4.2.7 Analyses of the Objectives

##### 4.2.7.1 Primary Effectiveness Variable

The primary objective of this study is to estimate the SVR12 rates in HCV patients treated according to the ABBVIE regimen.

Therefore the simple percentage of patients achieving SVR12 (for definition see section 4.1.1) will be calculated and a two-sided 95% confidence interval (CI) of the percentage will be computed based on the Wilson's Score method.

The primary effectiveness analysis on clinical outcomes will be performed on all patients in the CP stratified by genotype and cirrhosis status and overall.

In the framework of sensitivity analyses the primary analyses will be repeated for the CPSFU. Furthermore, the SVR12 rates will be also determined for all patients of the NCP.

An overview of Tables is given in Table 9.

The layouts of the tables mentioned above are provided in Part II of the SAP (Table Shells).

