**Study Size:**

650 patients, recruited in approximately 50 sites

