## 9.7 Data Analysis

### 9.7.1 Analysis Population, Time Windows and Handling of Missing Data

The target population (TP) is defined as all patients who fulfill the criteria specified in Section 9.2.1. The core population (CP) is defined as all patients of the TP, who have started the treatment combination recommended in the current local label for their disease characteristics. Patients not receiving the treatment recommended in the local label will be summarized in the non-core population (NCP). In addition, the core population with sufficient follow-up data (CPSFU) is defined as all CP patients, who fulfil one of the following criteria:

- (1) evaluable HCV RNA data  $\geq 70$  days after the last actual dose of the ABBVIE REGIMEN (i.e. data within the SVR12 time window)
- (2) a HCV RNA value  $\geq 50$  IU/mL at the last measurement post-baseline (i.e. no virological response achieved at the last measurement on-treatment or post-treatment)
- (3) HCV RNA  $< 50$  IU/mL at the last measurement post-baseline, but no HCV RNA measurement  $\geq 70$  days after the last actual dose of the ABBVIE REGIMEN due to reasons related to safety (e.g. dropped out due to AE) or incomplete efficacy information (e.g. virologic failure such as relapse is reported in the eCRF but date and value of the corresponding HCV RNA test is missing). This means only patients who had virological response at their last on-treatment or post-treatment measurement, but had no HCV RNA measurements  $\geq 70$  days post-treatment for reasons not related to safety or effectiveness (e.g. lost-to-follow-up or patient not willing to perform an additional HCV RNA test  $\geq 70$  days post-treatment) will be excluded from this analysis.

The Safety Population (SP) is defined as all patients who received at least one dose of the ABBVIE REGIMEN.

In accordance with the non-interventional nature of the study all HCV RNA measurements will be performed at the sole discretion of the physician and all HCV RNA measurements have to be entered into the eCRF. All recorded HCV RNA values will be assigned to appropriate time points (baseline, on-treatment visits, EoT visit, post-treatment visits). The time windows for the assignments will be specified in the statistical analysis plan (SAP).

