### **9.9 Limitations of the Research Methods**

The limitations of observational studies, such as uncontrolled confounding by lack of randomization, and difficulties to clearly interpret treatment effects in the context of missing data are well known. Their validity can be increased by accurate outcome measurements, documentation of the most common confounders, sufficient length of follow-up and by activities to obtain complete recording of available data as well as by searches for missing key data.

The most important outcome measure in this study is HCV RNA. Missing or unrecorded follow-up HCV RNA data can in particular lead to an underestimation of the real SVR rate as compared to the SVR rate of interventional trials. Highly sensitive and quantitative diagnostic tests are required to measure HCV RNA levels in blood. In an observational study each center will be using its own test – either commercially available or so-called “home-brew” tests – which might change from one visit to the next within a patient data set. The challenge is to accurately and consistently document test properties such as the LLoD and the ILLoQ to put the results into perspective of prior outcomes from

randomized controlled trials with (usually) central laboratory assessments for all trial participants.

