**Figure 1 - Study Flowchart**

### 3.2 Sample Size Calculation

In studies investigating the interferon-free ABBVIE REGIMEN  $\pm$  RBV, SVR12 rates of about 95% were observed, even in difficult-to-treat CHC patients (e.g. cirrhotic G1a treatment experienced patients). To describe in routine clinical practice the effectiveness of the ABBVIE REGIMEN  $\pm$  RBV in patients with CHC a precise estimate of the SVR12 rates in the core population of this study should be achieved (see Section 4.2.1 for the definition of the core population).

It is expected, that during the planned recruitment period of 12 months about 650 patients with ABBVIE REGIMEN  $\pm$  RBV can be included into this observational study, and that at least 620 patients will be evaluable in the core population. As obvious from Table 1, if the SVR12 rate is at least 95%, then with 620 patients the width of the 95% confidence interval (CI) will not be wider than 3.5%. Even in the case that fewer patients will be enrolled and only 590 patients can be evaluated in the core population, the 95% CI will have a width of  $\leq 3.6\%$  for a SVR12 rate of 95%.

**Table 1** Width of 95% Confidence Interval for SVR12

Number of patients	SVR12 rates	95% Confidence Interval*			Width
		Lower Limit	Upper Limit		
620	95%	93.0	96.5	3.5%	
590	95%	92.9	96.5	3.6%	
62	95%	86.5	98.3	11.8%	

\* exact two-sided 95% confidence interval according to Wilson's Score method

Assuming, that in total 620 patients will be evaluable, and subgroups of interest consist of at least 10% of the entire group (i.e.  $\geq 62$  patients), then the width of the 95% CI will be  $< 12\%$  for a SVR12 rate of 95%, which is also considered sufficiently precise for subgroup analyses.

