### **SVR12 (Exploratory Analyses)**

Univariate and multiple logistic regression (MLR) methods will be used to investigate the impact of various explanatory covariates (patient and disease characteristics) at baseline on SVR12.

These analyses will be of exploratory nature, data driven, and will be performed for CP population. Univariate logistic regression will be performed first and then backward selection procedures will be applied to generate the final MLR model. A p-value  $<0.05$  will be used for the covariates to stay in the model in a backward elimination step. If the percentage of patients with available data for a variable is lower than 80% of the patient group analyzed, then this variable will not be considered in the MLR analysis.

The variables to be considered are as follows:

- Key demographic information
  - Age (continuous)
  - Gender (Female [reference], Male)
  - Race/ethnic origin (White/Caucasian [reference], Black, Asian/Oriental, Other [all other races]); at least two categories with at least 10% of the patients each have to exists, so that this variable will be considered
  - Weight (continuous)
  - BMI (continuous)
  - IL28B, rs12979860 (CC [reference], CT or TT); patients with unknown genotype are excluded from the respective analyses.
- CHC disease characteristics
  - Years since diagnosis (continuous)
  - Mode of CHC infection (Drug use [reference], Other [all other answers excluding unknown], unknown);
  - Most recent stage of liver fibrosis (No cirrhosis/Transition to cirrhosis [reference], Cirrhosis; for definition see 4.2.6.2);
  - HCV RNA level at baseline ( $\log_{10}$  IU/mL)
  - HCV genotype (G1a\*, G1b, G4; for definition see section 4.2.6.2)
  - Type of treating institute (Private Practice / Private Hospital, Academic / University Hospital, General Hospital, Other)
  - Co-infections (every patient not reporting the respective co-infection is considered as not having the respective co-infection)
    - HIV (No [reference], Yes)
    - HBV (No [reference], Yes)
  - Liver and/or CHC related co-morbidities (every patient not reporting the respective co-morbidity is considered as not having the respective co-morbidity)
    - Liver transplantation (No [reference], Yes)
    - Steatosis (non-alcoholic) (No [reference], Yes)
    - Decompensated liver disease (No [reference], Yes)
  - Other co-morbidities (every patient not reporting the respective co-morbidity is considered as not having the respective co-morbidity)

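### The SVR12 intervals and logistic models take about 620 patients from about 50 sites as independent; if outcomes correlate within site, the overall interval is too narrow and type of treating institute is tested with too small an error

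*SAP*

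**What the plan says.** **Size.** The protocol abstract plans "650 patients, recruited in approximately 50 sites". SAP 3.2 expects that "at least 620 patients will be evaluable in the core population" and concludes that "with 620 patients the width of the 95% confidence interval (CI) will not be wider than 3.5" percentage points if SVR12 is at least 95%. A fallback of 590 patients gives a width of at most 3.6. All three rows of SAP Table 1 use the patient count as the sample size.

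**Intervals.** SAP 4.2.7.1 takes the simple percentage, and "a two-sided 95% confidence interval (CI) of the percentage will be computed based on the Wilson's Score method". SAP 4.2.7.2.1 uses the same method for the other response rates.

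**Regressions.** SAP 4.2.7.2.1 plans univariate and then multiple logistic regression with backward elimination, where p<0.05 keeps a covariate. One candidate is "Type of treating institute (Private Practice / Private Hospital, Academic / University Hospital, General Hospital, Other". SAP 4.2.4 treats institution type as site information. The adherence models follow the same methods.

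**Role of the site.** Protocol 9.7.1 says "all HCV RNA measurements will be performed at the sole discretion of the physician", and Protocol 9.9 says "In an observational study each center will be using its own test". Under SAP 4.2.3, an SVR12 value still missing after flanking and backward imputation counts as virological failure.

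Neither document mentions a site effect, a cluster-robust variance, a design effect or an ICC.

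**The concern.** The Wilson interval and ordinary logistic regression both assume that patients are independent. Here the recorded outcome depends partly on the site. A site that follows patients up less closely records more failures, because some patients have no HCV RNA result that can be used for SVR12. Sites also differ in case mix: SAP 4.2.4 lists transplant, drug-user and HIV/HCV co-infection units among the unit types. Protocol 9.2.4 wants the sites to represent national practice, so between-site variation belongs in the uncertainty of the estimate.

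Two results are exposed. The first is the overall CP interval, on which the sample size rests. The second is type of treating institute. It does not vary within a site, so its information comes from about 50 sites rather than 620 patients. Predictive factors are a secondary objective, and a p-value decides which stay in the model. Too small an error therefore makes a spurious institute effect more likely to be retained and reported.

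**Working it through.** **1. Reproduce the plan's table.** Wilson score interval without continuity correction, p = 0.95, z = 1.96:

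- n = 620: 92.99 to 96.46, width 3.47 (plan 3.5)
- n = 590: 92.93 to 96.49, width 3.55 (plan 3.6)
- n = 62: 86.49 to 98.26, width 11.77 (plan 11.8)

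The table is correct under independence.

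**2. Design effect for the overall CP.** Patients per site: m = 620/50 = 12.4. With CV the coefficient of variation of site size, deff = 1 + ((1 + CV²)·m − 1)·ICC, and effective n = 620/deff. ICC and CV are assumptions. With equal sites (CV = 0), deff = 1 + 11.4·ICC:

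| ICC | deff | effective n | width, points |
|---|---|---|---|
| 0 | 1.00 | 620 | 3.47 |
| 0.01 | 1.11 | 557 | 3.66 |
| 0.02 | 1.23 | 505 | 3.85 |
| 0.05 | 1.57 | 395 | 4.37 |
| 0.10 | 2.14 | 290 | 5.12 |

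The width passes 3.6 at an ICC of about 0.007 and 4.0 at about 0.028. With very unequal sites (CV = 1.0) it is 3.86, 4.23 and 5.19 at ICC 0.01, 0.02 and 0.05.

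**3. Coverage and false positives.** Beta-binomial simulation with 50 sites, 620 patients, true SVR12 95% and 20,000 runs. The test is a naive 5% likelihood-ratio test of a null two-category covariate, with 25 sites in each category:

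| ICC | coverage, equal sites | coverage, CV 1.0 | false positives, equal sites | false positives, CV 1.0 |
|---|---|---|---|---|
| 0 | 94.8% | 94.7% | 5.2% | 5.0% |
| 0.01 | 93.2% | 92.0% | 6.5% | 7.8% |
| 0.02 | 91.9% | 89.3% | 7.6% | 10.3% |
| 0.05 | 87.8% | 82.5% | 11.9% | 17.4% |

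**4. Four categories.** The SAP has four institute categories (3 degrees of freedom). As an approximation, a nominal 5% test rejects with probability P(χ²₃ > 7.815/deff). With equal sites this is 9.5% at ICC 0.02 and 17.3% at 0.05. A simulation with an assumed split of sites over the four categories gave about 11% and 19%, against 6% with essentially no clustering.

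**5. Subgroups.** A subgroup of 62 spread evenly over 50 sites has 62/50 = 1.24 patients per site. At ICC 0.05, deff = 1 + 0.24 × 0.05 = 1.012, and the width is 11.85 instead of 11.77.

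**6. What an ICC near 0.02 means.** Suppose 5 of 50 sites record 85% and the others 96.1%, so that the mean is 95%. Then ICC = 0.1 × 0.9 × 0.111² / (0.95 × 0.05) = 0.023. This is about 12.4 × 0.111 = 1.4 extra failures at each of five sites.

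**The case against.** **Nothing in the documents shows a positive ICC.** This is correct. A reader might infer that the intervals are too narrow as planned, but the documents support only the conditional statement. At ICC 0.01 with equal sites the width grows by only about 0.2 points.

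**Several provisions weaken the route from site to outcome.** Backward imputation carries a later HCV RNA value into the SVR12 window, so late testing alone does not create a failure. A common rule requires a detection or quantification limit of at most 50 IU/mL, and Protocol 9.9 adds that the test may change between visits of one patient. The assay is therefore a weak source of clustering. The sensitivity analysis in core patients with sufficient follow-up excludes responders lost for reasons unrelated to safety or effectiveness. These points stand, but patients never tested again still count as failures in the CP, which is the primary population. The sensitivity analysis also assumes independence.

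**Not all intervals are affected alike.** A reader might infer that every planned interval is materially wrong. Step 5 shows otherwise for thinly spread subgroups; the effect is larger only where a subgroup is concentrated in few sites.

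**The regressions are exploratory, and the size of the error depends on the test.** In a separate two-category simulation at ICC 0.02, the naive Wald test rejected 6.4% and the sandwich Wald test 5.6%, a small gain. At ICC 0.05 the figures were 10.0% and 6.2%. The SAP does not name the test. The exploratory label lowers the stakes but does not correct the standard error.

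**The primary objective is descriptive.** No threshold or decision depends on a few tenths of a point. This limits the weight of the interval issue.

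**Conclusion.** The concern holds in conditional form. The plan treats patients as independent throughout, and within-site correlation is plausible because of discretionary testing and the failure rule for missing values. If it is present, the overall CP interval understates uncertainty and type of treating institute is tested with too small an error.

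For an assumed ICC of 0.01 to 0.05 with equal sites, the loss is modest to moderate for the interval: 0.2 to 0.9 points of width, and coverage of 93% down to 88%. It is more serious for the institute covariate, where a nominal 5% test of two categories rejects 6.5% to 12% of the time. Four categories or unequal site sizes raise that rate. These figures rest on the assumed ICC, 12.4 patients per site and a true SVR12 of 95%.

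**What to change.** **SAP 4.2.7.1.** For overall CP SVR12, report the site ICC and a site-clustered interval beside the Wilson interval. This can be Wilson at the effective sample size or a bootstrap that resamples sites. The estimated design effect is noisy: in simulation at ICC 0.02 with 50 near-equal sites, its 5% to 95% range was 0.85 to 1.69, and it was at or below 1 in 20% of runs. State in advance that an estimate below 1 will not be used to narrow the interval.

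If this is extended to genotype or cirrhosis strata, use each stratum's own number of patients per site. Applying the whole-CP design effect of 1.57 (ICC 0.05) to 62 thinly spread patients would give a width of 15.2 points instead of about 11.8.

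**SAP 4.2.7.2.1.** Fit the SVR12 and adherence logistic models with site as the cluster: GEE or a sandwich variance with small-sample correction, or a random site effect. Name the test, and use it for elimination, at minimum for type of treating institute.

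**Cost.** SAP wording, a few lines of code and slightly wider intervals. No new data are needed, because site information is already recorded. If the ICC turns out close to zero, the added analysis supports the planned interval.

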##### 4.2.7.2 Secondary Variables

###### 4.2.7.2.1 Secondary Effectiveness Variables

###### Response

For the other response rates (i.e. RVR, SVR24 , SVR48, EoT response rate, relapse rate, viral breakthrough), the simple percentage of patients and a two-sided 95% confidence interval (CI) of the percentage will be computed (based on the Wilson's score method) as well. The RVR and EoT response rates will be reported for CP and the SVR24 and SVR48 rates will be reported for the respective CPSFU, stratified by genotype and cirrhosis status and overall. The relapse rates will be estimated stratified by SVR window (i.e. during SVR12 window=relapse12, during SVR24

window=relapse24, after SVR24 window=relapselate) and stratified by genotype and cirrhosis status and overall in patients of the CP with EoT response who fulfilled the following criteria:

- completed treatment as defined previously,
- had at least one HCV RNA measurement  $\geq 70$  days post-treatment or was a treatment failure between EoT and 70 days post-treatment.

Viral breakthrough rates [defined as at least one documented HCV RNA  $<50$  IU/mL followed by HCV RNA  $\geq 50$  IU/mL during treatment] will be estimated overall and stratified by genotype and cirrhosis status in all patients of the CP, who have at least one undetectable or unquantifiable, on-treatment HCV RNA measurement and at least one on-treatment or EoT measurement thereafter.

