### 9.3.2 Secondary Variables

- 
- Type of treatment regimen (± Dasabuvir, ± RBV, intended and actual combination, dose and duration)
- Patient adherence
- Serious and non-serious adverse events and pregnancy occurrences
- Questionnaire scores on PROs: Chronic Illness Therapy-Fatigue (FACIT-F), Work Productivity and Activity Impairment (WPAI), Burden of Suffering (PRISM), Patient Activation Measure (PAM-13)
- Co-morbidities and concomitant medication
- HCV relapse or reinfection after achieving SVR12 until post treatment week 48

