**Core Population with Sufficient Follow-up [CPSFU {12, 24, 48}]**

In addition, the core population with sufficient follow-up data regarding SVR12, SVR24 or SVR48, respectively, is defined as all CP patients,

- who have evaluable HCV RNA data  $\geq 70$  days,  $>126$  days or  $>210$  days, respectively, after the last actual dose of the ABBVIE REGIMEN
- or a HCV RNA value  $\geq 50$  IU/mL at the last measurement post-baseline
- or had HCV RNA  $<50$  IU/mL at the last measurement post-baseline, but no HCV RNA measurement  $\geq 70$  days,  $>126$  days or  $>210$  days, respectively, after the last actual dose of the ABBVIE REGIMEN due to reasons related to safety (e.g. dropped out due to adverse event) or virologic failure (e.g. virologic failure such as relapse is reported in the electronic case report form (eCRF) but date and value of the corresponding HCV RNA test is missing).

This means only (1) patients who had virological response at their last on-treatment or post-treatment measurement, but had no post-treatment HCV RNA measurements  $\geq 70$  days,  $>126$  days or  $>210$  days, respectively, for reasons not related to safety or effectiveness (e.g. lost-to-follow-up or patient not willing to perform an additional HCV RNA test  $\geq 70$  days,  $>126$  days or  $>210$  days post-treatment, respectively) and (2) patients who had no post-baseline HCV RNA measurements for reasons not related to safety or effectiveness, and (3) patients with missing end of treatment date for reasons not related to safety or effectiveness, will be excluded from this analysis.

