#### 4.2.3 Handling of missing data

No data will be imputed for any effectiveness or safety analyses except for the analyses of the HCV RNA endpoints and certain PRO endpoints. The discussion of missing data imputation for the PRO endpoints is included in section 4.2.7.2.3.

HCV RNA values will be selected for an RVR, EOTR and SVR analysis based on visit windows as defined in Table 4. When there is no HCV RNA value in a visit window based on defined visit windows, the closest values before and after the window, regardless of the value chosen for the subsequent and preceding window, will be used for the flanking imputation described below. For analysis of RVR, EOT and SVR, if a subject has a missing HCV RNA value at a post-Day 1 visit but with undetectable or unquantifiable (LLoD or LLoQ  $\leq$ 50 IU/mL) HCV RNA levels at both the preceding value and succeeding value, the HCV RNA level will be considered undetectable or unquantifiable, respectively, at this visit for this subject. In addition, if a subject has an

unquantifiable HCV RNA level at the preceding value and an undetectable HCV RNA level at the succeeding value, or vice versa, the HCV RNA level will be imputed as unquantifiable at this visit for this subject.

For analyses of RVR, subjects still missing a value for the visit after flanking imputation will be considered as a failure. For EoTR and SVR analysis, if there is no value in the appropriate window after flanking imputation but there is an HCV RNA value after the window, then it will be imputed into the EoTR or SVR window respectively. Subsequent to this flanking and backward imputation, if the HCV RNA value remains missing at a specific time point, then the subject will be considered as virological failure at this time point (i.e., not undetectable or unquantifiable).

If a subject starts another treatment for HCV, then all HCV RNA values for this subject measured on or after the start date of the new HCV treatment will be excluded from analyses. The subject will be considered a failure for summaries of viral response at all time points after the start of the new HCV treatment.

Due to the non-interventional nature of this study several different methods for determination of the HCV RNA value can be applied. For the purpose of the statistical analysis, a HCV RNA measurement is considered <50 IU/mL,

- if a PCR test was used

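### SVR24 and SVR48 are reported in sets that keep documented virologic failures but drop untested responders, so they fall with loss to follow-up, and the protocol's post-SVR12 recurrence variable is only partly analysed

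*SAP*

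**What the plan says.** Three rules in the SAP and one line in the protocol bear on this.

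- **Analysis set.** SAP 4.2.7.2.1 says that "the SVR24 and SVR48 rates will be reported for the respective CPSFU, stratified by genotype and cirrhosis status and overall". The core population (CP) is named for rapid and end-of-treatment (EoT) response, not for these two rates. SVR12 is analysed in the CP and, as a sensitivity analysis, in CPSFU12 (SAP 4.2.7.1). SAP Table 8 lists the response rates as a single CP/CPSFU output by genotype and cirrhosis status.
- **Membership.** Under SAP 4.2.1 a CP patient enters CPSFU24 or CPSFU48 with a test after day 126 or day 210 respectively, or with an HCV RNA value of at least 50 "IU/mL at the last measurement post-baseline". A patient also enters if the last value was below 50 and the later test is missing because of safety or virologic failure. Patients whose last value was below 50 and who lack the later test are removed when this is "for reasons not related to safety or effectiveness (e.g. lost-to-follow-up or patient not willing to perform an additional HCV RNA test", and so on.
- **Missing values.** SAP 4.2.3 applies flanking imputation, then fills an empty SVR window from a later value. If the value is still missing, "then the subject will be considered as virological failure at this time point".
- **Protocol variable.** Protocol 9.3.2 lists "HCV relapse or reinfection after achieving SVR12 until post treatment week 48". SAP 4.1.2 has no such entry. SAP 4.2.7.2.1 does plan relapse rates split into the SVR12 window, the SVR24 window (relapse24) and the time after it (relapse_late). Their denominator is CP patients with EoT response who completed treatment and either had a test at day 70 or later or failed before then.

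**The concern.** Failures and responders meet different entry conditions. A patient whose last value was at or above 50 IU/mL stays in CPSFU48 without any test after day 210. A patient who reached SVR12 stays only if tested again, apart from the safety and virologic-failure exceptions. HCV RNA testing is left to the physician's routine practice (SAP 4.2.2), so untested responders must be expected. As they leave, a fixed group of failures is divided by a shrinking total, and the rate falls with no recurrence at all.

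With SVR12, SVR24 and SVR48 in one output, a decline can be read as late loss of response. Strata with poorer follow-up can look as if cure were less durable there. The variable the protocol set up to answer this question directly, recurrence in patients who had achieved SVR12, is not carried into the SAP's list.

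**Working it through.** **Inputs.** SAP 3.2 expects that "at least 620 patients will be evaluable in the core population" and states that "SVR12 rates of about 95% were observed". Taking 95% of 620 gives R = 589 responders and 31 non-responders. Two inputs are not in the documents and are varied as assumptions:

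- t, the share of SVR12 responders tested after day 210
- F, the number of the 31 non-responders kept in the CPSFU

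**Reproducing the plan's own figure.** SAP Table 1 describes its interval as "exact two-sided 95% confidence interval according to Wilson's Score method". The Wilson score interval has centre (p + z²/2n)/(1 + z²/n) and half-width z√(p(1−p)/n + z²/4n²)/(1 + z²/n). With p = 0.95 and z = 1.96 it gives:

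- n = 620: 92.99 to 96.46, width 3.47
- n = 590: 92.93 to 96.49, width 3.55
- n = 62: 86.49 to 98.26, width 11.77

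All three rows agree with the table after rounding.

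**SVR48 in CPSFU48 with no late recurrence.** The rate is R·t / (R·t + F). It assumes that no responder is kept untested for a safety reason; any such patient would count as a failure and lower the rate further. At t = 100% it equals SVR12 in CPSFU12.

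| Kept failures F | t = 100% | 80% | 60% | 50% | Fall, 100% to 50% | Wilson 95% CI at 50% |
|---|---|---|---|---|---|---|
| 31 | 95.0% | 93.8% | 91.9% | 90.5% | 4.5 points | 86.8–93.2 |
| 20 | 96.7% | 95.9% | 94.6% | 93.6% | 3.1 points | 90.4–95.8 |
| 10 | 98.3% | 97.9% | 97.2% | 96.7% | 1.6 points | 94.1–98.2 |

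For example, with F = 31 and t = 50%: 294.5 / (294.5 + 31) = 90.5%. In a subgroup of 62 with 59 responders and 3 kept failures, the rate goes from 59/62 = 95.2% to 29.5/32.5 = 90.8%.

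**Comparison with SVR12 in the CP.** There the rate is 589/620 = 95.0% whatever the split of the 31. SVR48 is below 95% only if F > R·t/19 = 31·t. At t = 50% the threshold is 15.5, so 20 kept failures give a lower figure (93.6%) and 10 give a higher one (96.7%).

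**SVR24.** CPSFU24 admits any test after day 126, and a value after day 210 fills an empty SVR24 window. The share that matters is therefore those tested at any time after day 126, which cannot be smaller than t. SVR24 is pulled down no more than SVR48, and usually less.

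**Windowed relapse rates.** No test in the later window is needed to be in the denominator, so untested patients count as free of relapse. With an assumed true late relapse rate of 2% and 40% untested, the reported rate is 2% × 0.6 = 1.2%.

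**Recurrence among SVR12 responders with a later test.** With no recurrence, durability is 100% at any t. The Wilson lower limit is 99.4%, 99.2%, 98.9% and 98.7% for t = 100%, 80%, 60% and 50%. Lower testing costs precision but does not move the estimate.

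**The case against.** Much can be said for the plan as written. SVR48 is not conditional on SVR12, so keeping known failures is coherent. The obvious alternative, the full CP with missing counted as failure, would be far worse: 589 × 0.8/620 = 76.0% at 80% tested and 47.5% at 50%. SAP 4.2.5 tabulates CPSFU membership and exclusion reasons by genotype and cirrhosis status, so unequal loss can be seen. Protocol 9.9 warns that missing follow-up HCV RNA can depress the SVR rate. The table shells (SAP Part II) are not among the documents, so a footnote cannot be ruled out. All this limits the harm, but nothing in the available text says that SVR12 and SVR48 are not comparable, and the disposition counts do not correct the rate.

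Three stronger readings are tempting, and the documents do not support them.

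- **Durability goes unanalysed.** It does not: relapse24 and relapse_late are planned with Wilson intervals, by genotype, cirrhosis status and overall. What is missing is narrower. The denominator is not SVR12 achievers and leaves out those who stopped treatment early, no later test is required, and post-treatment reinfection is not addressed.
- **Every SVR12 non-responder is retained.** Only documented virologic failures, and patients untested for safety or virologic-failure reasons, are kept. Those who fail SVR12 merely through missing data for other reasons leave the CPSFU. F = 31 is thus the upper end.
- **SVR48 must fall below the primary SVR12 rate.** The F > 31·t condition shows that the sign can go either way against the CP rate. The downward pull is certain only against SVR12 in CPSFU12.

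**Conclusion.** The point holds for the SVR24 and SVR48 rates in the CPSFU and is worth correcting. The downward pull follows from SAP 4.2.1, 4.2.3 and 4.2.7.2.1 together and needs no recurrence to appear. At 50% late testing it amounts to about 1.6 to 4.5 points for SVR48 with 10 to 31 kept failures, set against a planned SVR12 interval 3.5 points wide. The size rests on two quantities that the documents do not give, the late-testing share and the number of kept failures, and on the planned 620 patients at 95%. Two strata with the same cure rate but different testing could show, at the 31-in-620 failure ratio, 93.8% (80% tested) against 90.5% (50% tested).

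The windowed relapse rates do not settle the matter, because they err in the opposite direction and are not conditional on SVR12. The protocol's post-SVR12 variable is therefore partly covered, not wholly omitted. The affected endpoints are secondary and descriptive; the primary SVR12 analysis in the CP is untouched.

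**What to change.** Add the protocol's variable to SAP 4.1.2 and 4.2.7.2.1. Among CP patients who achieved SVR12 and have at least one HCV RNA value after day 126, and separately after day 210, report the number and percentage with a value of at least 50 IU/mL (relapse or reinfection). Give the Wilson 95% CI, by genotype and cirrhosis status and overall, and show beside it the number of SVR12 responders with no later test. Use this as the durability result. Footnote SVR24 and SVR48 in the CPSFU as not directly comparable with SVR12, because documented failures are retained while untested responders are removed.

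The cost is SAP wording and one further table from data already collected. The drawback is a denominator limited to responders who were tested. Testing is at the physician's discretion, so they may differ from those who were not; the count of untested responders makes that limit visible.
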